Week 2 (Visit 2): Participants will complete items listed in Table 1, Week 2 (Visit 2). The study physician will determine if the participant is eligible for a dose increase. Research staff (i.e. research coordinators/research assistants) will dispense medication to the participant based on the direction from the study physician/prescription from the study physician for the next six weeks of the study. For remote participants, medication for the remaining six weeks of the study will be mailed out as well as medication for discontinuation by research staff with appropriate temperature monitoring.

Week 4 (Visit 3): Participants will complete items listed in Table 1, Week 4 (Visit 3).

Week 8 (Visit 4): Participants will complete items listed in Week 8 (Visit 4). The study physician will also discuss transition of care (see below) and/or medication continuation. Participants will also have their blood drawn and may be asked to participate in the optional fMRI scan.

Optional Post-Study (Week 10): Clinical visit with physician if the participant is discontinuing the study medication and/or as needed. If a participant chooses to continue with the study medication, he/she will be asked to follow up with his/her most responsible physician (MRP) for ongoing care and this post-study visit would not be needed. Participants will be informed prior to signing the consent form that research staff/research physician will not be able to tell them if they received drug or placebo when they finish the study at week 8 and they will have to wait until the entire study is complete to find out.

Table 1. Study schedule with assessments

Study Visit	Screening (Visit 0)	Baseline (Visit 1)	Visit 2	Visit 3	End-of-study (Visit 4)
Week	(-1 to -21 days from baseline)	0	2 (+/- 2 days)	4 (+/- 2 days)	8 (+/- 2 days)
Consent	X				
Inclusion/Exclusion	X				
Demographics	X				
Past COVID-19 Infection Information	X				

M.I.N.I 7.0.2	X				
Psychiatric/Medical History	X				
Lifestyle Factors	X				
Current Medications	X	X	X	X	X
Medication Changes	X	X	X	X	X
Adverse Events		X	X	X	X
Anthropometrics		X	X		X
MoCA		X			
SETS		X			
DSST		X	X		X
TMT-A/B		X	X		X
RAVLT		X	X		X
CogState Online Cognitive Battery**		X	X		X
PDQ-20		X	X	X	X
GAD-7		X	X	X	X
SHAPS		X	X	X	X
FSS		X	X	X	X
WHO-5		X	X	X	X
SDS		X	X	X	X
BAS		X	X	X	X
EQ-5D-5L		X	X	X	X
QIDS-SR16		X	X	X	X
IPAQ		X		X	X
PCFS	X	X	X	X	X
EEfRT		X			X

Physician Assessment*	X		X	X	X
Laboratory assessments		X			X
fMRI + Cognitive Test		X			X

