Abbreviations: ^a: BAS: Behavioural Activation Scale; DSST: Digit Symbol Substitution Test; EQ-5D-5L: 5-Level EQ-5D version; fMRI: functional magnetic resonance imaging; FSS: Fatigue Severity Scale; GAD-7: Generalized Anxiety Disorder, 7-item; IPAQ: International Physical Activity Questionnaire; EEfRT: Effort Expenditure for Rewards Task ; M.I.N.I: Mini-International Neuropsychiatric Interview; MoCA: Montreal Cognitive Assessment; PCFS: Post-Covid Functional Scale; PDQ-20: Perceived Deficits Questionnaire, 20-item; Quick Inventory of Depressive Symptomatology (16-Item) (Self-Report) (QIDS-SR16); RAVLT: Rey's auditory verbal learning test; RPE: Borg Rating of Perceived Exertion Scale; SDS: Sheehan Disability Scale; SETS: Stanford Expectations of Treatment Scale; SHAPS: Snaith-Hamilton Pleasure Scale; TMT-A/B: Trails Making Test-A/B; WHO-5: World Health Organization Well-Being Index, 5-item.

*One physician assessment will be conducted between the baseline and screening visit.

**May be conducted remotely.

Sample Size

- Total recruitment N=200 (i.e., 100 subjects allocated to vortioxetine [5-20 mg] and placebo each).
- The target sample size is based on effect sizes reported by previous clinical trials that evaluated the efficacy of antidepressants vs placebo and nutraceuticals in individuals with chronic fatigue syndrome ^{6,23-25}.
- The effect size of vortioxetine on DSST-measured cognitive function is estimated at approximately 0.2-0.5 ^{26,27}. Previous experience without patients enrolled in clinical trials (investigator-initiated trials) with vortioxetine as part of the THINC-it tool validation indicated that vortioxetine improves measures of processing speed (the prominent domain validated by the DSST) of significance with a sample size of 200.
- It is then estimated that a sample size of 100 per treatment arm would detect clinically relevant change with vortioxetine treatment on DSST as the dependent measure ^{27,31}.

Feasibility

- It is estimated, based on prior general population research conducted by the BCDF, that recruitment will take approximately 12 months.
- Community research ethics board approval, 2-4 weeks (BCDF is an independent research center not requiring university- or hospital-based REB reviews).

Description of Study Procedures

Efficacy Assessments

Digit Symbol Substitution Test (DSST)

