All data outlined in Table 1 will be collected for all participants up until and including the time of withdrawal from the study. Recruitment will occur for this study on an ongoing basis until 200 participants are recruited and have completed the study. Participants withdrawn from the study will follow the outlined “Transition to Standard Care” and “Medication Discontinuation Process” outlined below.

Participant Compensation

Compensation for In-Person Participants

Participants will receive \$125 CAD at week 2 visits, \$125 at week 4 visits and \$250 at week 8 visit. Participants may also choose to receive the full \$500 at the end of the study (week 8).

Participants who complete the EEfRT task will be awarded their earnings from this task in addition to the \$500. The EEfRT may also be administered as a stand alone assessment (i.e., outside of fMRI) or as part of the fMRI assessment. Participants who complete the EEfRT will be compensated with what they earn from this task in addition to the \$500. Participants that complete exploratory blood work will also be compensated \$50.

Compensation for Remote Participants

Participants will receive \$31.25 CAD at week 2 visits, \$31.25 at week 4 visits and \$62.50 CAD at week 8 visit. Participants may also choose to receive the full \$250 at the end of the study (week 8).

Study Medication: Vortioxetine

AGE: 18-64

Participants receiving vortioxetine will be provided 10 mg/day on days 1–14 of the treatment period, and will be titrated to 20 mg/day at the start of week 3 (day 15) based on study clinician judgment. For the remaining 6 weeks, the dose of vortioxetine will be 20 mg/day, unless adjudicated otherwise by a study clinician.

AGE: >65

Per product monograph, participants 65+ receiving vortioxetine will be provided 5 mg/day on days 1–14 of the treatment period, and will be titrated to 10 mg/day at the start of week 3 (day 15) based on study clinician judgment. For the remaining 6 weeks, the dose of vortioxetine will be 10 mg/day, unless adjudicated otherwise by a study clinician.

Age: 65

Individuals aged 65 may start at 5mg or 10mg on days 1-14, and this dose may be titrated to 10mg or 20mg, respectively, at the start of week 3 based on the recommendation of the study physician.

Vortioxetine will be encapsulated in a capsule shell made of Capsugel® empty hard gelatin capsule (non-porcine / pure-bovine origin). Colorant: Swedish Orange OpC307. Size: AA.

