- Hemorrhage (including contusion, ecchymosis, epistaxis, gastrointestinal or vaginal hemorrhage)

Please see product monograph for full details.

Contraindications

Hypersensitivity to vortioxetine or any components of the formulation. Angioedema has been reported in patients treated with vortioxetine. The use of monoamine oxidase inhibitors (MAOI) intended to treat psychiatric disorders with vortioxetine or within 21 days of stopping treatment with vortioxetine is contraindicated because of an increased risk of serotonin syndrome. The use of vortioxetine within 14 days of stopping an MAOI intended to treat psychiatric disorders is also contraindicated.

Starting vortioxetine in a patient who is being treated with MAOIs or antibiotics such as linezolid or intravenous methylene blue is also contraindicated because of an increased risk of serotonin syndrome.

Storage

Medication will be stored at room temperature in a locked cabinet and office space at BCDF ([name]).

Transition to Standard of Care

Patients will be informed of the transition to standard of care procedures (outlined here) post study prior to providing consent to participate in the study. These procedures will also be outlined in writing in the patient consent form itself.

Upon completing the 8-week course of vortioxetine, if patients benefit from this drug, they will be encouraged to continue the treatment with their most responsible physician (MRP). Patients will be notified prior to study consent that not all drug plans will cover the cost of vortioxetine. Should patients wish to continue to use this drug post-study when they do not have coverage, they will be personally responsible for the costs.

If patients do experience side effects during the study, the study physician will make a recommendation regarding the discontinuation or dose reduction of the medication for the

remainder of the study. If participants do not experience any improvement upon study completion in mood or cognition, the medication will be gradually discontinued over a two-week period upon study completion (end of week 8). Participants will take half of their final dose of vortioxetine during the first week post-study and no medication during the second week of discontinuation. Participants will be provided with one week worth of medication for this discontinuation process but will not be provided any further supply thereafter.

Vortioxetine discontinuation process

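### Week 8 advice to continue vortioxetine does not allow for the placebo arm, and the protocol text does not have the prescriber told that trial exposure is unknown (minor; no effect on the analysis)

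*Combined protocol and SAP*

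**What the plan says.** Transition to Standard of Care addresses everyone who finishes as if all had taken the drug: "Upon completing the 8-week course of vortioxetine, if patients benefit from this drug, they will be encouraged to continue the treatment". Their own physician takes over the prescribing. The taper applies in the opposite case: "If participants do not experience any improvement upon study completion in mood or cognition", medication is withdrawn over two weeks.

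Sample Size gives the allocation as "100 subjects allocated to vortioxetine [5-20 mg] and placebo each". Optional Post-Study (Week 10) says that participants learn before consenting that study staff "will not be able to tell them if they received drug or placebo when they finish the study at week 8", and that they must wait for the end of the entire study. Withdrawal Procedures and Next Steps keeps recruitment open "until 200 participants are recruited and have completed the study".

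At Week 8 (Visit 4) the study physician will "discuss transition of care (see below) and/or medication continuation". A participant who continues is referred to their own physician "for ongoing care and this post-study visit would not be needed".

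Study Medication: Vortioxetine starts ages 18-64 on 10 mg/day for days 1-14, after which the dose "will be titrated to 20 mg/day at the start of week 3 (day 15) based on study clinician judgment". Participants over 65 go from 5 to 10 mg/day, and those aged exactly 65 may follow either schedule. Later changes are left to the study clinician.

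On the taper, Week 2 (Visit 2) has remote participants' discontinuation supply mailed with the six-week treatment supply. Transition to Standard of Care sets the taper at half the final dose. Vortioxetine discontinuation process has it provided at the end of week 8, at half the current dose.

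**The concern.** For someone who took placebo and improved, there is nothing to continue. The advice would lead to a new start on vortioxetine, and neither the participant nor the outside prescriber can know this at the time. A prescriber asked to carry on an eight-week treatment could reasonably prescribe the dose the participant reports, and so omit the lower starting dose that the trial gives its own new users.

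The first weeks are when tolerability matters most. The Side effects section lists gastrointestinal events at 21-32% and places their peak in the first week. Within the trial a new user has physician assessments at weeks 2 and 4 (Table 1). After the trial none is scheduled for someone who continues. The exclusion criteria also admit some participants on a subtherapeutic dose of another antidepressant and call the combination investigational. A placebo participant in that group would meet the combination for the first time outside the trial.

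What is at stake is participant safety after the primary endpoint has been measured.

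**Working it through.** The plan gives no figure for placebo participants encouraged to continue, so there is none to reproduce. The check sets the sections side by side and then sizes the group.

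**Step 1: does the rule reach placebo participants?** The advice depends on perceived benefit, not on allocation. Allocation is 100 and 100, and it is not disclosed at week 8. No sentence in the transition, week 8, week 10 or discontinuation text deals with a placebo participant who improves. Followed as written, the rule includes them.

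**Step 2: would it be their first exposure?** For some, not all. The exclusion criteria remove only people with known intolerance or a previous failed trial of vortioxetine. Someone who took it before, tolerated it and did not fail on it may enrol.

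**Step 3: how long is exposure unknown?** Feasibility estimates about 12 months of recruitment. A participant among the first enrolled would finish about 12 months before the last one does, so disclosure usually comes well after the prescribing decision.

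**Step 4: what share of those encouraged had placebo?** Let p0 and p1 be the proportions judged to benefit on placebo and on drug, with equal numbers per arm at week 8. Then

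share = p0 / (p0 + p1), with p1 = Φ(Φ⁻¹(p0) + d).

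Inputs: d = 0 (no effect); d = 0.2 and 0.5 (the range under Sample Size); d = 3.1 / 8.0 = 0.3875 (the power calculation in the Statistical analysis plan, which states 0.38). p0 is an assumption, taken from 20% to 60%. These values of d refer to DSST, whereas the transition text speaks of mood or cognition, so this is an illustration.

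| p0 | d = 0 | d = 0.2 | d = 0.3875 | d = 0.5 |
|---|---|---|---|---|
| 0.20 | 50.0% | 43.4% | 38.1% | 35.3% |
| 0.40 | 50.0% | 45.5% | 42.0% | 40.1% |
| 0.60 | 50.0% | 47.1% | 44.8% | 43.7% |

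Example: p0 = 0.40 and d = 0.3875 give p1 = 0.553, so the share is 0.40 / 0.953 = 42.0%. In words, half or somewhat fewer.

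**Step 5: what does omitting the starting dose mean?** For ages 18-64, 14 × 20 = 280 mg over the first two weeks instead of 14 × 10 = 140 mg. For over 65, 14 × 10 = 140 mg instead of 14 × 5 = 70 mg. The first dose is doubled in each case.

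**Step 6: the remote taper.** Assume the supply mailed at week 2 is half of a planned 20 mg, that is 20 / 2 = 10 mg. If the dose is later cut to 10 mg, the taper should be 10 / 2 = 5 mg. The mailed taper is then 10 / 10 = 100% of the final dose, where 50% is intended.

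**The case against.** The strongest reply is that several safeguards already exist.

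- Participants are told before consent that allocation will stay unknown, and the transition procedures are explained in the consent form, so they can tell their own physician.
- The study physician discusses continuation at week 8.
- Placebo participants passed the same screening for hypersensitivity, interacting drugs, mania, angle closure glaucoma, hyponatremia and bleeding.
- Study Site has a medical file opened for every participant, in which the study physician records visits.
- Those who continue are referred to a physician for ongoing care, and the week 10 visit remains available as needed.
- No one is exposed without a new prescription, possibly at their own cost.

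A handover letter may also exist outside the protocol, and the consent form cannot be seen.

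Most of this stands, and it is why the point is minor. It does not close the gap. A prescriber protects a new user only if aware that the person may be one, and the protocol text leaves that to the participant's account.

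A second reply is that the shares in the working rest on an assumed benefit rate and do not count people prescribed or harmed. That is correct. Only the statement that about half or somewhat fewer would have had placebo should be relied on.

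On the taper, the dedicated discontinuation section already ties the dose to the current one. A late dose cut makes the mailed treatment capsules wrong as well, so new supply would be needed anyway. The worst case shown is one more week at a dose already being taken, and the protocol states that the drug causes no discontinuation syndrome. The conflict between sections is real but very small.

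**Conclusion.** The point holds as a minor participant-safety issue. The written advice covers placebo participants who improve. It could lead to their being newly started on vortioxetine, possibly at twice the trial's starting dose, with no study visit scheduled and no instruction that the prescriber be told exposure is unknown. By 1:1 allocation, about half or somewhat fewer of those encouraged would have had placebo, assuming similar retention in the two arms. The number who would obtain a prescription, and the dose they would be given, cannot be derived from the documents.

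A reader might infer more, and three stronger readings are not supported. First, that every placebo participant who improves would be new to the drug: some past use is allowed. Second, that participants are misled about allocation: the protocol discloses before consent that it will remain unknown. Third, that the trial result is affected: the advice takes effect after the week 8 assessment and touches neither the analysis, the sample size nor the type I error.

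**What to change.** In Transition to Standard of Care, replace *continue the treatment* with *discuss starting or continuing vortioxetine*.

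Give the participant, or send the most responsible physician, a short neutral note: *Allocation is blinded until the study is complete, so exposure to vortioxetine during the trial is unknown. The trial's starting dose was 10 mg/day (5 mg/day over 65; either at 65) for 14 days. The dosing choice is yours.*

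For the taper, add to Week 2 (Visit 2) that any dose change after week 2 for a remote participant triggers a replacement taper at half the new dose, sent with the replacement treatment supply.

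The cost is one phrase, one note template and one sentence, and the blind is kept. The clinical downside is that some participants who improved on active drug may be re-titrated and spend two weeks at a lower dose (for example 10 mg instead of 20 mg, or 5 mg instead of 10 mg). For that reason the note states the facts and does not recommend restarting at the lower dose.
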